APPENDIX 4 WOMEN OF CHILDBEARING POTENTIAL DEFINITIONS AND METHODS OF CONTRACEPTION

DEFINITIONS

Woman of Childbearing Potential (WOCBP)

A woman is considered fertile following menarche and until becoming post-menopausal unless permanently sterile. Permanent sterilization methods include hysterectomy, bilateral salpingectomy, and bilateral oophorectomy.

Women in the following categories are not considered WOCBP

- Premenarchal
- Premenopausal female with 1 of the following:
 - Documented hysterectomy
 - Documented bilateral salpingectomy
 - Documented bilateral oophorectomy

Note: Documentation can come from the site personnel's review of the participant's medical records, medical examination, or medical history interview.

- Postmenopausal female
 - A postmenopausal state is defined as 12 months of amenorrhea in a woman over age 45 years in the absence of other biological or physiological causes. In addition, females under the age of 55 years must have a serum follicle stimulating hormone, (FSH) level > 40 mIU/mL to confirm menopause.

Note: Females treated with hormone replacement therapy, (HRT) are likely to have artificially suppressed FSH levels and may require a washout period in order to obtain a physiologic FSH level. The duration of the washout period is a function of the type of HRT used. The duration of the washout period below are suggested guidelines and the investigators should use their judgement in checking serum FSH levels.

- 1 week minimum for vaginal hormonal products (rings, creams, gels)
- 4 week minimum for transdermal products
- 8 week minimum for oral products

Other parenteral products may require washout periods as long as 6 months. If the serum FSH level is > 40 mIU/ml at any time during the washout period, the woman can be considered postmenopausal.

CONTRACEPTION GUIDANCE FOR FEMALE PARTICIPANTS OF CHILDBEARING POTENTIAL

One of the highly effective methods of contraception listed below is required during study duration and until the end of relevant systemic exposure, defined as 5 weeks (33 days) after the end of study treatment, plus 30 days.

Local laws and regulations may require use of alternative and/or additional contraception methods.

| |
|---|
| 
Highly Effective Contraceptive Methods That Are User Dependent
 
Failure rate of <1% per year when used consistently and correctly.^a
 |
| 
 • Combined (estrogen- and progestogen-containing) hormonal contraception associated with inhibition of ovulation^b 
 – oral – intravaginal – transdermal |
| 
 • Progestogen-only hormonal contraception associated with inhibition of ovulation^b 
 – oral – injectable |
| 
Highly Effective Methods That Are User Independent
 |
| 
 • Implantable progestogen-only hormonal contraception associated with inhibition of ovulation^b • Intrauterine device (IUD)^c • Intrauterine hormone-releasing system (IUS)^c • Bilateral tubal occlusion |
| 
 • Vasectomized partner 
A vasectomized partner is a highly effective contraception method provided that the partner is the sole male sexual partner of the WOCBP and the absence of sperm has been confirmed. If not, an additional highly effective method of contraception should be used.
 |
| 
 • Sexual abstinence 
Sexual abstinence is considered a highly effective method only if defined as refraining from heterosexual intercourse during the entire period of risk associated with the study treatment. The reliability of sexual abstinence needs to be evaluated in relation to the duration of the study and the preferred and usual lifestyle of the participant.
 
 • It is not necessary to use any other method of contraception when complete abstinence is elected. • WOCBP participants who choose complete abstinence must continue to have pregnancy tests, as specified in Section 2. • Acceptable alternate methods of highly effective contraception must be discussed in the event that the WOCBP participants chooses to forego complete abstinence |

NOTES:

- ^a Typical use failure rates may differ from those when used consistently and correctly. Use should be consistent with local regulations regarding the use of contraceptive methods for participants participating in clinical studies.
- ^b Hormonal contraception may be susceptible to interaction with the study treatment, which may reduce the efficacy of the contraceptive method. Hormonal contraception is permissible only when there is sufficient evidence that the IMP and other study medications will not alter hormonal exposures such that contraception would be ineffective or result in increased exposures that could be potentially hazardous. In this case, alternative methods of contraception should be utilized.
- ^c Intrauterine devices and intrauterine hormone releasing systems are acceptable methods of contraception in the absence of definitive drug interaction studies when hormone exposures from intrauterine devices do not alter contraception effectiveness

Less Than Highly Effective Contraceptive Methods That Are User Dependent

Failure rate of >1% per year when used consistently and correctly.

- Male or female condom with or without spermicide. Male and female condoms cannot be used simultaneously
- Diaphragm with spermicide
- Cervical cap with spermicide
- Vaginal Sponge with spermicide
- Progestogen-only oral hormonal contraception, where inhibition of ovulation is not the primary mechanism of action

Unacceptable Methods of Contraception

- Periodic abstinence (calendar, symptothermal, post-ovulation methods)
- Withdrawal (coitus interruptus)
- Spermicide only
- Lactation amenorrhea method (LAM)

CONTRACEPTION GUIDANCE FOR MALE PARTICIPANTS WITH PARTNER(S) OF CHILDBEARING POTENTIAL

Male participants with female partners of childbearing potential are eligible to participate if they agree to the following during the treatment and until the end of relevant systemic exposure.

- Inform any and all partner(s) of their participation in a clinical drug study and the need to comply with contraception instructions as directed by the investigator.
- Male participants are required to use a condom for study duration and until the end of relevant systemic exposure defined as 93 days after the end of treatment in the male participant.
- Female partners of males participating in the study to consider use of effective methods of contraception until the end of relevant systemic exposure, defined as 93 days after the end of treatment in the male participant.
- Male participants with a pregnant or breastfeeding partner must agree to remain abstinent from penile vaginal intercourse or use a male condom during each episode of penile penetration during the treatment and until 93 days after the end of treatment.

- Refrain from donating sperm for the duration of the study treatment and for 93 days after the end of treatment.

COLLECTION OF PREGNANCY INFORMATION

Guidance for collection of Pregnancy Information and outcome of pregnancy on the Pregnancy Surveillance Form is provided in [Section 9.2.5](#) and the Appendix for Adverse Events and Serious Adverse Events Definitions and procedures for Evaluating, Follow-up and Reporting

APPENDIX 5 DIAGNOSTIC CRITERIA FOR DRUG AND ALCOHOL ABUSE

The following is taken from DSM-IV:

Diagnostic Criteria for Psychoactive Substance Dependence

A maladaptive pattern of substance use, leading to clinically significant impairment or distress as manifested by 3 (or more) of the following, occurring at any time in the same 12-month period:

1. Tolerance, as defined by either of the following:
 - a) A need for markedly increased amounts of the substance to achieve intoxication or desired effect,
 - b) Markedly diminished effect with continued use of the same amount of the substance.
2. Withdrawal, as manifested by either of the following:
 - a) The characteristic withdrawal syndrome for the substance,
 - b) The same (or closely related) substance is taken to relieve or avoid withdrawal symptoms.
3. The substance is often taken in larger amounts or over a longer period than was intended.
4. There is a persistent desire or unsuccessful efforts to cut down or control substance use.
5. A great deal of time is spent in activities necessary to obtain the substance (eg, visiting multiple doctors or driving long distances), use the substance (eg, chain-smoking) or recover from its effects.
6. Important social, occupational or recreational activities are given up or reduced because of substance use.
7. The substance use is continued despite knowledge of having a persistent or recurring physical or psychological problem that is likely to have been caused or exacerbated by the substance (eg, current cocaine use despite recognition of cocaine-induced depression, or continued drinking despite recognition that an ulcer was made worse by alcohol consumption.)

Criteria for Severity of Psychoactive Substance Dependence

Mild: Few, if any, symptoms in excess of those required to make the diagnosis, and the symptoms result in no more than mild impairment in occupational functioning or in usual social activities or relationships with others.

Moderate: Symptoms or functional impairment between “mild” and “severe”.

Severe: Many symptoms in excess of those required to make the diagnosis, and the symptoms markedly interfere with occupational functioning or with usual social activities or relationships with others.

In Partial Remission: During the past 6 months, some use of the substance and some symptoms of dependence.

In Full Remission: During the past 6 months, either no use of the substance, or use of the substance and no symptoms of dependence.

Diagnostic Criteria for Psychoactive Substance Abuse

- A. A maladaptive pattern of psychoactive substance use, leading to clinically significant impairment or distress as manifested by 1 (or more) of the following, occurring at any time in the same 12-month period:
1. Recurrent substance use resulting in a failure to fulfill major role obligations at work, school, or home (eg, repeated absences or poor work performance related to substance use; substance-related absences, suspensions, or expulsions from school, neglect of children or household).
 2. Recurrent substance use in situations in which it is physically hazardous (eg, driving an automobile or operating a machine when impaired by substance use).
 3. Recurrent substance-related legal problems (eg, arrests for substance-related disorderly conduct).
 4. Continued substance use despite having persistent or recurrent social or interpersonal problems caused or exacerbated by the effects of the substance (eg, arguments with spouse about consequences of intoxication, physical fights).
- B. The symptoms have never met the criteria for substance dependence for this class of substance.

2 STUDY DESCRIPTION

2.1 Study Design

This is a Phase 1, open-label, randomized, 2-period, 2-treatment crossover study in healthy participants. Healthy male or female participants as determined by medical history, physical examination, vital signs, 12-lead electrocardiogram (ECG), and clinical laboratory tests will be

eligible to participate in the study. Participants will undergo screening evaluations to determine eligibility within 28 days prior to study treatment administration. On Day -1, participants will enter the clinical facility and be confined for the duration of the study, until discharge on Day 8. Prior to dosing on Day 1 of Period 1, participants will be randomly assigned to 1 of 2 treatment sequences (AB or BA, where Treatment A is 5 × 0.5-mg apixaban tablets and Treatment B is 25 × 0.1-mg apixaban sprinkle capsules) in a 1:1 ratio. Participants will receive a single oral dose of apixaban on Days 1 and 5. There will be a 4-day washout period between doses. Treatments A and B will be prepared in the pharmacy.

The study design schematic is presented in [Figure 2.1-1](#).

D = Study Discharge; E = Enrollment; R = Randomization; S = Screening; Treatment A = 5 × 0.5-mg apixaban tablets; Treatment B = 25 × 0.1-mg apixaban sprinkle capsules; W = Washout

Physical examinations, vital sign measurements, 12-lead ECG, and clinical laboratory evaluations will be performed at selected times throughout the study. Participants will be closely monitored for adverse events (AEs) throughout the study. Blood samples will be collected for up to 72 hours after study drug administration for pharmacokinetic (PK) analysis. Approximately 240 mL of blood will be drawn from each participant during the study.

Participants will complete a palatability assessment immediately (within 5 minutes) after administration of the apixaban 0.5-mg tablet and 0.1-mg sprinkle capsule dosages, on both Day 1 and Day 5.

2.2 Treatment Assignment

Eligible participants will be randomized in a 1:1 ratio to 1 of 2 treatment sequences according to a computer-generated randomization scheme prepared by PPD.

Study treatment will be administered on Days 1 and 5.

Enrolled participants, including those not dosed, will be assigned sequential participant numbers starting with 00001, (eg, 00001, 00002, 00003.... 00010). Those enrolled participants meeting

inclusion and exclusion criteria will be eligible to be randomized. Randomization numbers will be assigned prior to dosing.

Participants will not be replaced if they are discontinued from the study secondary to an AE unless the AE can be determined to be unrelated to treatment. The Sponsor (or designee) may replace participants for other reasons. If a participant is replaced after dosing then the replacement participant will be assigned the original participant's number plus 100. The replacement participant will receive the same treatments as the participant being replaced but a new randomization number will be assigned to him or her. For example, Participant 4 would be replaced by Participant 104.

2.3 Blinding and Unblinding

This is an open-label study.

2.4 Protocol Amendments

This statistical analysis plan (SAP) reflects the administrative letter, dated 12 April 2018.

3 OBJECTIVES

3.1 Primary

The primary objective for this study is to assess the bioavailability of apixaban 0.1-mg sprinkle capsules relative to apixaban 0.5-mg tablets, both administered orally in healthy participants.

3.2 Secondary

The secondary objectives for this study are:

- To assess the safety and tolerability of apixaban
- To assess the PK of apixaban 0.1-mg sprinkle capsules
- To assess the PK of apixaban 0.5-mg tablets

4 ENDPOINTS

4.1 Efficacy Endpoints

There are no planned efficacy endpoints.

4.2 Safety Endpoints

Safety endpoints include incidence of nonserious AEs, serious AEs (SAEs), AEs leading to discontinuation or death, as well as marked abnormalities in clinical laboratory tests, vital sign measurements, 12-lead ECGs, and physical examinations.

4.3 Pharmacokinetic Endpoints

Pharmacokinetic parameters of apixaban will be derived from the respective plasma concentration versus time data. Individual PK parameter values will be derived by non-compartmental methods by a validated PK analysis program using actual times.

The primary PK endpoints are:

- C_{max}, AUC(INF), and AUC(0-T) of apixaban.

The secondary PK endpoints are:

- T_{max}, T-HALF, and Frel of apixaban.

Specific PK parameters are shown in [Table 4.3-1](#).

Table 4.3-1: Pharmacokinetic Parameters, Naming Conventions and Definitions

Parameter	Definition
C _{max}	Maximum observed plasma concentration
T _{max}	Time of maximum observed plasma concentration
AUC(0-T)	Area under the plasma concentration-time curve from time zero to time of last quantifiable concentration
AUC(INF)	Area under the plasma concentration-time curve from time zero extrapolated to infinite time
T-HALF	Terminal plasma half-life
Frel	Relative bioavailability

5 SAMPLE SIZE AND POWER

The similarity of the bioavailability will be concluded if the 90% confidence interval (CI) for the ratio of geometric means of apixaban 0.1-mg sprinkle capsules relative to apixaban 0.5-mg tablets are wholly contained within 80% and 125% for C_{max} and AUC. The following table shows the power provided with data from 28 PK evaluable participants based on different assumptions of difference between the bioavailability of apixaban 0.1-mg sprinkle capsules and apixaban 0.5-mg tablets.

True Geometric Mean Ratio	Power of Cmax	Power of AUC(0-T)	Power of AUC(INF)	Overall Power
1	99%	99%	99%	97%
1.02	99%	99%	99%	97%
1.04	98%	99%	99%	96%
1.06	96%	99%	99%	94%
1.08	91%	99%	99%	89%
1.1	83%	99%	99%	81%

As an example, if there is a 10% difference between the bioavailability of apixaban 0.1-mg sprinkle capsules and apixaban 0.5-mg tablets, then data from 28 PK evaluable participants will provide approximately 83%, 99%, and 99% power to conclude similar bioavailability for Cmax, AUC(INF), and AUC(0-T), respectively. The overall power for this hypothesis is approximately 81%.

These calculations use the approach described by Diletti et al.⁵ and assume Cmax and AUC are log normally distributed with intra-subject coefficient of variation (%CV) of 18% for Cmax and 12% for AUC, as estimated from apixaban Study CV185111⁴ and Study CV185292⁶. To allow for possible dropouts, a total of 30 participants are planned to be randomized to obtain at least 28 PK-evaluable participants.

6 STUDY PERIODS, TREATMENT REGIMENS AND POPULATIONS FOR ANALYSES

6.1 Study Periods

- The pre-treatment period will be from the time the Informed Consent Form (ICF) is signed until the time just prior to dosing on Day 1 for all participants. The pre-treatment period should be no longer than 28 days and will include all screening, enrollment, Day -1, randomization, and Day 1 predose procedures.
- Period 1 will be from the time of dosing on Day 1 until the time prior to dosing in the next period on Day 5, or until study discharge due to premature discontinuation if the participant is not dosed on Day 5.
- Period 2 will be from the time of dosing on Day 5 until the participant is discharged on Day 8, or until the day of study discharge due to premature discontinuation after dosing on Day 5.
- If a participant is not discharged on Day 8, any data collected after Day 8 will be assigned to the post-treatment period.
- Periods 1 and 2 will be considered on-therapy for the purpose of safety analyses.

The definition of each study period is included in [Table 6.1-1](#).

Table 6.1-1 Definition of Study Period

PERIOD SEQUENCE	PERIOD NAME	DATE TO BE USED	DEFINITION
1	PRE-TREATMENT	- CONSENT DATE - DOSE DATETIME ON DAY 1	Starting with consent date and ending by (<) dose date and time on Day 1
2	PERIOD 1	- DOSE DATETIME ON DAY 1 - DOSE DATETIME ON DAY 5	Starting with dose date and time on Day 1 and ending by (<) dose date and time on Day 5
3	PERIOD 2	- DOSE DATETIME ON DAY 5 - DISCHARGE DATE	Starting with dose date and time on Day 5 and ending by (≤) discharge date
4	POST-TREATMENT	- DISCHARGE DATE	Starting with discharge date + 1

6.2 Treatment Regimens

The following treatments will be administered in this study with a 1:1 ratio in sequences of AB and BA.

- Treatment A = 5 × 0.5-mg apixaban tablets
- Treatment B = 25 × 0.1-mg apixaban sprinkle capsules

6.3 Populations for Analyses

- Enrolled Population, defined as all participants who signed the ICF.
- Randomized Population, defined as all participants who are randomized to a sequence of treatments.
- Treated Population, defined as all participants who received at least 1 dose of study treatment.
- Pharmacokinetic Population, defined as all participants who received at least 1 dose of study treatment and had any available concentration-time data. Pharmacokinetic listings and PK parameter calculations will be based on this population.
- Evaluable PK Population is a subset of the Pharmacokinetic population. The Evaluable PK population includes all participants who had adequate PK profiles for accurate estimation of PK parameters and had no protocol deviations considered to affect the PK assessments.

All available derived PK parameter values will be included in the PK data set and reported, but only participants with evaluable PK data will be included in the summary statistics and statistical analysis.

7 STATISTICAL ANALYSES

SAS® version 9.3 or higher will be used for statistical analyses, tabulations and graphical presentations.

7.1 General Methods

All data recorded on case report forms (CRFs) will be listed by participant. Descriptive summaries will be presented for continuous variables using number of participants (N), mean, standard deviation (SD), median, minimum and maximum. Geometric mean and %CV will also be presented for sample plasma PK parameters. Descriptive summaries for categorical variables will utilize counts and percentages.

Where appropriate, baseline is defined as the last non-missing result with a collection date-time less than the date-time of the first dose of study treatment.

Adverse events and medical history will be coded according to the most recent Medical Dictionary for Regulatory Activities (MedDRA) version. Previous and concomitant medications will be coded using the World Health Organization (WHO) Drug Dictionary, version to be delineated in the clinical study report (CSR).

7.2 Study Conduct

Deviations from the study protocol, protocol amendments, and administrative changes will be documented. No potential protocol deviations are defined as being relevant in this healthy volunteer study; listing of relevant protocol deviations will not be provided.

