7.1 Treatments Administered

The selection and timing of dose for each participant is as follows:

Table 7.1-1: Selection and Timing of Dose

| Study Treatment | Unit Dose Strength(s)/Dosage Level(s) | Dosage Formulation Frequency of Administration | Route of Administration |
|---|---------------------------------------|--|-------------------------|
| Apixaban 0.5-mg tablets (Treatment A) | 5 × 0.5 mg | Single dose on Day 1 or Day 5 | Oral |
| Apixaban 0.1-mg sprinkle capsules (Treatment B) | 25 × 0.1 mg | Single dose on Day 1 or Day 5 | Oral |

In the morning on Days 1 and 5, each participant will receive a single oral dose of apixaban after fasting for at least 8 hours. Participants will fast for at least 4 hours after study treatment administration on Days 1 and 5.

Treatment A will be administered as 5 × 0.5-mg apixaban tablets; the tablets will be dissolved in water, and the entire apixaban solution must be consumed. Procedures for preparation and administration of the 5 × 0.5-mg apixaban tablets will be provided in the pharmacy manual.

Treatment B will be administered as 25 × 0.1-mg apixaban sprinkle capsules; the capsules will be opened and contents will be emptied into water, and the entire apixaban solution must be consumed. Procedures for preparation and administration of the 25 × 0.1-mg apixaban sprinkle capsules will be provided in the pharmacy manual.

Treatments A and B will be prepared in the pharmacy. Preparation and administration should occur within the established stability window. Additional details are available in the pharmacy manual.

The time of dose administration will be called “0” hour.

Restrictions related to food and fluid intake are described in [Section 6.3](#).

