10.3 Statistical Analyses

The statistical analysis plan will be developed and finalized before database lock and will describe the selection of participants to be included in the analyses, and procedures for accounting for missing, unused, and spurious data. Below is a summary of planned statistical analyses.

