7.7 Pharmacokinetics

The PK population will be used for all PK listings. The Evaluable PK population will be used for summary statistics and statistical analyses. Analysis will include all valid analyte data for apixaban.

Participant plasma concentration-time profiles will be listed and summarized by treatment and nominal collection time for apixaban. Plots of individual plasma concentration profiles over time will be provided. Overlays of individual plasma concentration profiles over time will be provided by treatment. Plots of mean (+SD) plasma concentration profiles versus time will be presented for apixaban, and all treatments will be superimposed on the same plot.

All individual PK parameters will be listed for apixaban including any exclusions and reasons for exclusion. Summary statistics will be tabulated for each PK parameter by treatment. Geometric means and %CV will be presented for C_{max}, AUC(0-T), AUC(INF), and F_{rel}. Medians and ranges will be presented for T_{max}. Means and SDs will be presented for other PK parameters (ie, T-HALF). Decimal place specifications for summary statistics are described in [Section 7.9](#).

A linear mixed effect model with treatment and period as fixed effects and participant as repeated measures will be fitted to the log-transformed PK parameters (C_{max}, AUC[0-T], and AUC[INF]) for use in estimation of effects and construction of CIs. Kenward-Rogers degrees of freedom will be specified in the model. Initial estimation of the variance/covariance will be based on an unstructured (UN) R matrix assuming no common variances or covariances; however, this UN matrix will be assessed and the more parsimonious compound symmetry (CS) R matrix will be imposed if assumptions of common variances and covariances are reasonable and can be supported by the data. Point estimates and 90% CIs will be exponentiated and results will be reported on the original scale.

Specific details with appropriate SAS code are provided below. Apixaban as 0.1-mg sprinkle capsules (Treatment B) is the test treatment and apixaban as 0.5-mg tablets (Treatment A) is the reference treatment in the analysis.

```
PROC MIXED DATA=PKDATA;  
  BY [log transformed PK parameter such as Cmax, AUC(INF), AUC(0-T)];  
  CLASS TREATMENT PERIOD USUBJID;  
  MODEL LOG_PK = PERIOD TREATMENT / SOLUTION DDFM=KR;  
  REPEATED TREATMENT / SUBJECT = USUBJID TYPE = UN R;  
  LSMEANS TREATMENT / CL ALPHA=0.1;  

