7.9.2 Pharmacokinetic Summaries

In-text Tables

For in-text PK tables, %CV will be reported as integers. For other statistics except for SDs, values of 100 or higher will be presented as integers, values of 10 - <100 will be displayed to 1 decimal place, and values of 1 - <10 will be displayed to 2 decimal places. Values less than 1 will be displayed to 3 decimal places. Ratios will also be displayed to 3 decimal places. Standard deviations will be reported to a precision of 1 decimal place more than the mean.

Handling of Non-Quantifiable Concentrations⁷

For the summaries of plasma concentration-time data, concentrations that are less than the lower limit of quantification (LLOQ) should be displayed as “< LLOQ” in the listings and be treated as missing in summary tables and plots. For the purpose of calculating PK parameters, predose concentrations that are less than LLOQ and concentrations prior to the first quantifiable concentration that are less than LLOQ will be set to zero, and all other concentrations less than LLOQ will be set to missing.

All available plasma concentration-time data and derived PK parameter values will be included in the PK data set and listed accordingly.

Treatment of Outliers

If the predose concentration for a profile is greater than 5% of C_{max}, then the PK parameters for that profile will be excluded from summaries and statistical analysis. Other individual plasma concentrations, if deemed to be anomalous, may be excluded from the analysis following

a review of available documentation (eg, bioanalytical report, clinical data). Any such exclusion will be clearly listed in the study report along with justification for exclusion.

Entire plasma concentration-time profiles for a participant may be excluded following review of available documentation (eg, bioanalytical report, clinical data). However, results of analysis with and without the excluded profiles may be presented in the study report. Any such exclusion will be clearly listed in the study report along with justification for exclusion.

Pharmacokinetic Exclusions

Pharmacokinetic Analysis, Reporting, and Exclusion criteria should follow the BMS PK Harmonization document Version 2.0. Specific guideline for exclusionary criteria for half-life and how other PK parameters are affected for exclusion is under section 6.2 of the BMS PK Harmonization document.

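### Does SAP 7.2, which defines no protocol deviation as relevant, leave the primary PK analysis set undetermined under SAP 6.3?

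*SAP*

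**What the plan says.** The decision rule is in SAP 5: "The similarity of the bioavailability will be concluded if the 90% confidence interval (CI) for the ratio of geometric means" lies within 80% to 125% for Cmax and AUC. SAP 6.3 fixes who enters that analysis: "only participants with evaluable PK data will be included in the summary statistics and statistical analysis". To be evaluable a participant needs an adequate profile and must have "had no protocol deviations considered to affect the PK assessments". Protocol 10.2 has the same criterion.

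SAP 7.2 says that deviations will be documented, and then: "No potential protocol deviations are defined as being relevant in this healthy volunteer study; listing of relevant protocol deviations will not be provided". Protocol 10.3 promises that the SAP "will describe the selection of participants to be included in the analyses".

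Other parts of the SAP bear on selection:

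- SAP 7.9.2 has one mandatory rule: a profile with a predose concentration above 5% of Cmax is excluded.
- SAP 7.9.2 also names missed doses, vomiting, diarrhea and incomplete profiles as grounds on which exclusion is allowed, and refers to the sponsor's PK Harmonization document for exclusion criteria.
- For whole profiles removed after review, SAP 7.9.2 says "results of analysis with and without the excluded profiles may be presented in the study report". It requires each exclusion after review, of a profile or a single concentration, to be listed with its justification.
- SAP 7.7: "All individual PK parameters will be listed for apixaban including any exclusions and reasons for exclusion".
- SAP 7.1 lists all CRF data by participant, and SAP 7.4 lists drug administration and non-study medication.

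**The concern.** If *relevant* in SAP 7.2 meant relevant to PK, the two sections would collide. A participant who drank only part of a dose would stay in under 7.2 and come out under 6.3. Such an event is conceivable: Protocol 7.1 says "the entire apixaban solution must be consumed", and Protocol 6.3.1 adds fasting, water and meal rules. Neither SAP section refers to the other, and apart from missed doses no visible text names the deviations meant. Two analysts could then build different analysis sets from the same data.

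The stakes would be real. Keeping a participant with a spoiled dose biases the ratio, which can produce a false failure or a false finding of similarity. A list of exclusions also does not show who had the same deviation and was kept.

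**Working it through.** **Reading the two sections together.** SAP 7.2 attaches *relevant* to a listing. It does not mention an analysis set and does not say that anyone stays in. SAP 6.3 asks whether a deviation affected the PK assessments. An analyst obeying both documents the deviation (7.2), judges its effect on PK (6.3), removes the participant if PK was affected (6.3), and lists the exclusion with its reason (7.7). At no step does obeying one section break the other. Even without the deviation clause, a part-swallowed dose could come out through the adequate-profile requirement in 6.3 or the review of clinical data allowed in 7.9.2.

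**Reproducing the plan's power.** Inputs from SAP 5: n = 28, limits 0.80 and 1.25, within-participant CV 18% (Cmax) and 12% (AUC).

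- σ = √ln(1 + CV²): 0.1786 for Cmax, 0.1196 for AUC.
- Cmax standard error = 0.1786 × √(2/28) = 0.0477, with 26 degrees of freedom and t = 1.706.
- Cmax at ratio 1.10: ln(1.25/1.10) / 0.0477 − 1.706 ≈ 0.97, a normal probability of about 0.83. The exact two one-sided tests value is 83.2% (plan: 83%).
- AUC at 1.10: 98.8% (plan: 99%). Overall: 0.832 × 0.988 × 0.988 = 81.2% (plan: 81%).

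**What one deviation could do.** Assumption, not in the documents: one of the 28 has exposure halved in one period. The simulation is a 2×2 crossover with a period effect, 14 per sequence and 100,000 trials per cell. It compares keeping that participant with removing that participant. Share of trials in which the Cmax conclusion differs:

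| True ratio | 0.90 | 0.95 | 1.00 | 1.06 | 1.10 |
|---|---|---|---|---|---|
| Test dose halved | 24.4% | 9.0% | 1.4% | 2.7% | 7.6% |
| Reference dose halved | 9.2% | 2.1% | 1.4% | 10.8% | 22.1% |
| Test dose reduced by 25% | 8.2% | 2.2% | 0.3% | 2.0% | 5.6% |

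For AUC, the largest shares among these ratios are 19.7% (test halved, 0.90) and 13.2% (reference halved, 1.10).

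**Baseline.** Removing one participant with no deviation effect changes the Cmax conclusion in 5.0% of trials at 0.90 and 4.1% at 1.10. Most of the 8.2% and 5.6% in the last row, and about half of the 7.6% in the first, is therefore of the size expected from losing any one participant.

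**A worked case at 0.90.** This uses a paired analysis without a period term. The SD of the log ratio is 0.1786 × √2 = 0.2525.

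- *Removed:* 27 participants with geometric mean ratio 0.90. Half-width = 1.706 × 0.2525/√27 = 0.083, so the 90% CI is 0.828 to 0.978.
- *Kept:* add one participant at 0.90 × 0.5 = 0.45. The mean log ratio is ln 0.90 + ln 0.5/28 = −0.130. The SD is √[(26 × 0.2525² + (27/28) × (ln 0.5)²)/27] = 0.280. Half-width = 1.703 × 0.280/√28 = 0.090, so the 90% CI is 0.802 to 0.961.

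Both intervals pass.

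**False similarity at true ratio 1.25, Cmax.** Removing the affected participant, as SAP 6.3 directs, gives 5.0%. Keeping that participant gives 9.1% (test halved) or 1.0% (reference halved). The rule as written is the one that holds the nominal rate.

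**The case for a change.** The strongest case is that SAP 7.2 never says *relevant* is only a reporting category, that most exclusions in SAP 7.9.2 are discretionary, and that the study is open label. Concentrations and treatment can be known when evaluability is judged, and no visible text requires the judgement before the model is run. The size can matter: with the test dose halved at a true ratio of 0.90, Cmax power is 52% if the participant is kept and 76% if removed. In a deliberate worst case, dropping the single highest test/reference ratio of 28 at a true ratio of 1.25 raises false similarity from 5.0% to 11.9%.

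The textual part of this stands. The deviations are not named, the cross-reference is missing, and showing results both ways is optional. A separate listing of deviations would also show whether like cases were treated alike, unless deviations are on the CRF and so already listed under SAP 7.1.

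It does not show that a stated rule gives a wrong result. The 11.9% describes choosing exclusions by outcome. No rule in the SAP permits that, and a listed reason would expose it. The 52% arises only if 7.2 overrides 6.3, which it does not claim to do. Doses are given in the clinic, and Protocol 7.6 requires a mouth check to verify that the whole solution was swallowed, so a half-consumed dose should be uncommon. A mandatory second run would add information but leave the primary analysis as it is.

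**Conclusion.** No change follows. This is a gap that the analysts can fill sensibly: assess documented deviations for their effect on PK under SAP 6.3, apply the predose rule and the cited sponsor document, and list every exclusion with its reason. That path needs no choice between SAP 7.2 and SAP 6.3.

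Planned power is unaffected. With 30 randomized, two participants can be lost before the number falls below 28. Going from 28 to 27 moves Cmax power at a ratio of 1.10 only from 83.2% to 81.9%.

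The remaining exposure depends on the assumed spoiled dose and on a true ratio away from 1. With one test dose halved, the Cmax conclusion differs in about 24% of trials at 0.90, 8% at 1.10 and 1% at 1.00, against the 4% to 5% at 0.90 and 1.10 that any single removal causes.

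The conclusion rests on reading *relevant* in SAP 7.2 as a reporting term, which its wording supports but does not state. The PK Harmonization document and the Data Presentation Plan were not available, so what they add on evaluability is unknown.
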